2.1 Primary Objective

The primary objective of ISR 14-04 is to evaluate the post-market performance of GORE® VIABAHN® Endoprosthesis for the treatment of in-stent restenosis of the superficial femoral artery in a primarily U.S. population (at least 75% of patients being treated in the U.S.).

2.2 Design Summary

This study is a prospective, multicenter, non-randomized single-arm study to evaluate the post-market performance of the GORE® VIABAHN® Endoprosthesis for the treatment of in-stent restenosis in the superficial femoral artery.

A minimum of 15 Clinical Investigative Sites (referred to as “Sites” in the remainder of this document) in the U.S. and a maximum of 5 OUS Sites will participate in this study. A total of 108 Subjects (a minimum of 81 Subjects from the U.S. and a maximum of 27 OUS Subjects) will be enrolled in this study with a limit of 30 Subjects per U.S. Site. A minimum of 20 Subjects (out of the total 108 Subjects) will be enrolled with lesion lengths of 230-270mm. The anticipated accrual period is 24 months assuming an accrual rate is approximately 4.5 Subjects per month.

Patients are to be enrolled into the study provided all inclusion and no exclusion criteria are met as specified in Section 4. Subjects will be evaluated through hospital discharge and will be scheduled for follow-up visits at 30 days and at 12, 24, and 36 months post-treatment. Accounting for the expected period of enrollment, the total estimated duration of the study is 60 months.

2.3 Definitions

Ankle Brachial Index: The ankle systolic pressure in the study limb divided by the highest brachial systolic pressure in either arm.

CONFIDENTIAL INFORMATION

MD133254 Statistical Analysis Plan Template
Revision #1
Doc Type: GC

Acute Procedural Success: Successful delivery of study device and complete coverage of the target lesion without a procedure- or device-related Serious Adverse Event prior to hospital discharge.

Major Amputation: Removal of the lower limb above the metatarsals in the study limb, resulting from a vascular event.

Patency: Blood flow through the study device.

Primary Patency: Patent blood flow through the study device, which requires either a PSVR measurement ≤ 2.5 or patent flow indicated by the Core Lab, and without repeat intervention.

Primary Assisted Patency: Blood flow through the study device regardless of repeat interventions to maintain patency prior to occlusion.

Secondary Patency: Blood flow through the study device regardless of repeat interventions to maintain or restore patency after occlusion.

Stent Integrity: Freedom from study device stent fracture which is clearly distinguishable on imaging from the previously implanted non-covered stent.

Target Lesion(s): Stenotic or occluded segment(s) within and adjacent to a previously implanted non-covered stent(s) (>30 days) in the superficial femoral artery. An adjacent lesion is an extension of the stenotic or occluded segment that is contiguous with that lesion within the previously implanted non-covered stent.

Target Lesion Revascularization (TLR): Repeat intervention within the study device and 5 mm proximal or distal to the edge of the study device to maintain or re-establish patency.

Toe Brachial Index: The toe systolic pressure in the study limb divided by the highest brachial systolic pressure in either arm.

2.4 Primary Endpoints

2.4.1 Primary Patency at 12 months Post-procedure

The primary effectiveness endpoint is Primary Patency at 12 months post-procedure. This will be estimated through 365 days along with a 95% confidence interval using Kaplan-Meier analysis. Equivalent analysis will be performed with regards to the primary patency partitioning the data by lesion length (< 230 mm and ≥ 230 mm). All results will be compared to that obtained in the RELINE study.

CONFIDENTIAL INFORMATION

MD133254 Statistical Analysis Plan Template
Revision#: 1
Doc Type: GC

2.4.2 Procedure or Device-related Serious Adverse Events Within 30 days of the Index Procedure

The primary safety endpoint is procedure- or device-related Serious Adverse Events within 30 days of the index procedure. The total number of events as well as the number of Subjects experiencing them will be tabulated along with a 95% confidence interval.

2.5 Secondary Endpoints

2.5.1 Acute Procedural Success

Acute Procedural Success is defined as successful delivery of the study device and complete coverage of the target lesion without a procedure- or device-related Serious Adverse Event prior to hospital discharge. This will be tabulated omitting all Subjects with unknown status.

2.5.2 Primary Patency

Primary patency is defined as patent blood flow through the study device, which requires either a PSVR measurement ≤ 2.5 or patent flow indicated by the Core Lab, without repeat intervention. Primary patency will be estimated at 30 days, 12, 24, and 36 months along with a 95% confidence interval using Kaplan-Meier analysis.

2.5.3 Primary Assisted Patency

Primary assisted patency is defined as blood flow through the study device regardless of repeat interventions to maintain patency prior to occlusion. Blood flow will require confirmation by the study Core Lab. Primary assisted patency will be estimated at 30 days, 12, 24 and 36 months along with a 95% confidence interval using Kaplan-Meier analysis.

2.5.4 Secondary Patency

Secondary patency is defined as blood flow through the study device regardless of repeat interventions to restore patency after occlusion. Blood flow will require confirmation by the study Core Lab. Secondary patency will be estimated at 30 days, 12, 24, and 36 months along with a 95% confidence interval using Kaplan-Meier analysis.

2.5.5 Freedom from Target Lesion(s) Revascularization (TLR)

Target Lesion Revascularization is defined as a repeat intervention within the study device and 5 mm proximal or distal to the edge of the study device to maintain or re-establish patency. Freedom from TLR will be estimated at 30

CONFIDENTIAL INFORMATION

MD133254 Statistical Analysis Plan Template
Revision#: 1
Doc Type: GC

days, 12, 24, and 36 months along with a 95% confidence interval using Kaplan-Meier analysis.

2.5.6 Freedom from Major Amputation

Major Amputation is defined as removal of the study limb above the metatarsals, resulting from a vascular event. Freedom from major amputation will be estimated at 30 days, 12, 24, and 36 months along with a 95% confidence interval using Kaplan-Meier analysis.

2.5.7 Change in Ankle-Brachial Index (ABI)

Ankle Brachial Index is defined as the ankle systolic pressure in the study limb divided by the highest brachial systolic pressure in either arm. The minimum, maximum, median, mean, and standard error will be reported for the change in ABI relative to that measured pre-procedure at 30 days, 12, 24, and 36 months. All values measured within the defined window will be used in calculation.

2.5.8 Change in Rutherford Category

The change in Rutherford Category, measured relative to that obtained pre-procedure, will be assessed at 30 days, 12, 24, and 36 months. The minimum, maximum, median, mean, and standard error will be reported as well as the counts for each outcome. All values measured within the defined window will be used in calculation.

2.5.9 Stent Fracture

Device stent fractures will be assessed by the study Core Lab through x-ray images. A table of all stent fractures, which are clearly distinguishable from previously implanted stents, will be reported at 12, 24, and 36 months. All values measured within the defined window will be used in tabulation.

2.6 Additional Analysis

2.7 Sample Size

CONFIDENTIAL INFORMATION

MD133254 Statistical Analysis Plan Template
Revision#: 1
Doc Type: GC

3 Study Treatment Arm

The GORE® VIABAHN® Endoprosthesis with Heparin Bioactive Surface (US); GORE® VIABAHN® Endoprosthesis with PROPATEN Bioactive Surface (EU); and subsequently referred to as GORE® VIABAHN® Endoprosthesis throughout this document.

4 Study Data Collection

4.1 Data Collection Methods

This study will report clinical data using the Medidata Rave® Clinical Data Management System (CDMS) web-based application. The CDMS will be the database of record for the protocol and subject to regulatory inspections. All users will be trained to use the CDMS and will comply with study-specific guidelines / instructions as well as applicable regulatory requirements.

Subject data will be collected using protocol-specific case report forms (CRF). Site staff will enter data directly into the CRF for transmission to the Sponsor. The Sites will be notified of any significant amendments to the CRFs.

4.2 Data Clarification and Correction

Once entered, data will be evaluated to ensure that it is complete, consistent, and logically sound. If changes to the data in the CDMS are required, all changes, reasons for changes, and persons making the changes will be captured in the CDMS's audit trail.

4.3 CRF Completion Schedule

CRFs will be completed as soon as reasonably possible during or following each Subject visit.

5 Statistical Analyses

5.1 Timing of Analyses

Reports will be prepared when follow-up is complete for endpoints of the study (e.g., 1-year, 2-year, and 3-year). Additional interim analyses and reports will be done in order to comply with regulatory reporting requirements. This will consist of, at a minimum, the physical characteristics of enrolled Subjects as well as tabulations of all interventions and adverse events. In addition, listings of all interventions and adverse events will be prepared.

CONFIDENTIAL INFORMATION

MD133254 Statistical Analysis Plan Template
Revision#: 1
Doc Type: GC

Once all Subjects have either completed 36 months of follow-up or been withdrawn from the study, a formal statistical analysis will be performed to evaluate all study endpoints.

5.2 Analysis Populations

Both of the following populations will be used for analyses of primary and secondary endpoints.

(1) Intent to treat (ITT) – All patients assigned to the study treatment, regardless of whether or not they received it or have any protocol violations.

(2) Per protocol (PP) – A subset of the ITT population consisting of Subjects receiving the study device which meet all inclusion and exclusion criteria and without any major protocol violations.

5.3 Pooling of Data

Data from all study Sites will be pooled on a clinical basis, *i.e.*, the study sites will follow a common protocol, the study will be monitored to assure compliance with the protocol and applicable government regulations, and the data collection and handling procedures will be the same at all study sites.

5.4 Primary Endpoints

5.4.1 Primary Effectiveness - Primary Patency at 12 Months Post-procedure

Both the ITT and PP populations will be used with the following decision rules for calculating the primary patency at 12 Months post-procedure.

CONFIDENTIAL INFORMATION

MD133254 Statistical Analysis Plan Template
Revision#: 1
Doc Type: GC

5.4.2 Primary Safety - Procedure or Device-related Serious Adverse Events Within 30 Days of the Index Procedure

Both the ITT and PP populations will be used with the following decision rules for calculating the serious adverse events within 30 days of the index procedure.

5.5 Secondary Endpoints

5.5.1 Acute Procedural Success

Both the ITT and PP populations will be used with the following decision rules for calculating the percentage of subjects experiencing the acute procedural success.

CONFIDENTIAL INFORMATION

MD133254 Statistical Analysis Plan Template
Revision#: 1
Doc Type: GC

5.5.2 Primary Patency

Both the ITT and PP populations will be used with the following decision rules for calculating the primary patency through Kaplan-Meier time to event analysis.

5.5.3 Primary Assisted Patency

Both the ITT and PP populations will be used with the following decision rules for calculating the primary assisted patency through Kaplan-Meier time to event analysis.

CONFIDENTIAL INFORMATION

MD133254 Statistical Analysis Plan Template
Revision#: 1
Doc Type: GC

5.5.4 Secondary Patency

Both the ITT and PP populations will be used with the following decision rules for calculating the secondary patency through Kaplan-Meier time to event analysis.

5.5.5 Freedom from Target Lesion(s) Revascularization (TLR)

Both the ITT and PP populations will be used with the following decision rules for calculating the secondary patency through Kaplan-Meier time to event analysis.

CONFIDENTIAL INFORMATION

MD133254 Statistical Analysis Plan Template
Revision#: 1
Doc Type: GC

5.5.6 Freedom from Major Amputation

Both the ITT and PP populations will be used with the following decision rules for calculating the secondary patency through Kaplan-Meier time to event analysis.

5.5.7 Change in ABI

All subjects from both the ITT and PP populations which have their ABI measured at the corresponding visit, will be used for calculating the change in ABI statistics at each visit window. At each time point, the change in ABI values (post procedures measurement – pre-procedure measurement) will be tabled showing at least the minimum, maximum, median, mean, and standard error of the values obtained.

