Nothing herein is to be disclosed in any way without the prior express
permission of W. L. Gore & Associates, Inc.

**Post-Approval Study of the GORE® VIABAHN® Endoprosthesis for the Treatment of
In-Stent Restenosis in the Superficial Femoral Artery**

Protocol Number: ISR 14-04

Protocol Date: December 10, 2015 (Revision 2)
April 10, 2015 (Original, Revision 1)

NCT Number: NCT02542267

W. L. Gore and Associates, Inc.
Medical Products Division

Nothing herein is to be disclosed in any way without the prior
express written permission of W. L. Gore & Associates, Inc.

Post-Approval Study of the GORE® VIABAHN® Endoprosthesis for the Treatment of
In-Stent Restenosis in the Superficial Femoral Artery

Protocol Number: ISR 14-04

Amendment 1 (Rev. 2)

W. L. Gore & Associates, Inc.
Medical Products Division

PROTOCOL SUMMARY

Study Title	Post-Approval Study of the GORE® VIABAHN® Endoprosthesis for Treatment of In-Stent Restenosis in the Superficial Femoral Artery
Protocol Number	ISR 14-04
IDE or PMA Number	Post approval w/PMA# P040037 S060
Sponsor	W. L. Gore & Associates, Inc. Medical Products Division [name] [contact]
Study Device	The GORE® VIABAHN® Endoprosthesis with Heparin Bioactive Surface (US); GORE® VIABAHN® Endoprosthesis with PROPATENT™ Bioactive Surface (EU); and subsequently referred to as GORE® VIABAHN® Endoprosthesis throughout this protocol.
Study Design	Prospective, multicenter, single-arm study
Study Objective	The objective is to evaluate post-market safety and effectiveness of GORE® VIABAHN® Endoprosthesis for treatment of In-Stent Restenosis of the SFA
Primary Endpoints	
Effectiveness Endpoint: Primary Patency at 12 months by Kaplan-Meier analysis
 
Safety Endpoint: Device- and procedure-related Serious Adverse Events within 30 days of the procedure

Secondary Endpoint(s)	
 • Acute Procedural Success • Primary Patency at 30 days, 12, 24, & 36 months • Primary Assisted Patency at 30 days, 12, 24, & 36 months • Secondary Patency at 30 days, 12, 24, & 36 months • Freedom from TLR at 30 days, 12, 24, & 36 months • Freedom from Major Amputation at 30 days, 12, 24, & 36 months • Change in Ankle-Brachial Index from pre-procedure at 30 days, 12, 24, & 36 months • Change in Rutherford Category from pre-procedure at 30 days, 12, 24, & 36 months • Stent Fracture Assessment at 12, 24, & 36 months

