3.2.3. Secondary Endpoints

The secondary endpoints for this study include:

- Acute Procedural Success
- Primary Patency at 30 days, 12, 24 and 36 months
- Primary Assisted at 30 days, 12, 24 and 36 months
- Secondary Patency at 30 days, 12, 24 and 36 months
- Freedom from Target Lesion Revascularization at 30 days, 12, 24 and 36 months
- Freedom from Major Amputation at 30 days, 12, 24 and 36 months
- Change in Ankle-Brachial Index from pre-procedure at 30 days, 12, 24 and 36 months
- Change in Rutherford Category from pre-procedure at 30 days, 12, 24 and 36 months
- Stent Fracture Assessment at 12, 24 and 36 months

4. Study Population

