4.2. Inclusion Criteria

Potential Subjects must meet all of the following Clinical Inclusion Criteria:

1. Patient is ≥ 18 years old at the time of informed consent signature
2. Patient is willing to give written informed consent
3. Patient has a previously implanted (>30 days) non-covered stent(s) located in the superficial femoral artery
4. Patient has life-style limiting claudication, resting leg pain or minor tissue loss (Rutherford Category 2-5)
5. Patient demonstrates an ABI ≤ 0.9 . If ABI > 0.9 or not measureable, patient is eligible for study if toe-brachial index (TBI) is ≤ 0.5
6. Patient is male, infertile female or female of childbearing potential with a negative beta hCG pregnancy test within 7 days of the index procedure
7. Patient is capable of complying with protocol requirements, including follow-up visits

Potential Subjects must meet all of the following Angiographic Inclusion Criteria:

1. Patient has $\geq 50\%$ in-stent restenosis and/or an occlusion in a previously implanted (>30 days) non-covered stent(s) located in the superficial femoral artery defined as beginning at least 1 cm below the origin of the profunda femoris artery and ending at least 1 cm above the intercondylar notch
2. Patient has a maximum total lesion length of 270 mm, consisting of in-stent and adjacent occlusive disease
3. Patient has a minimum of 1 cm of non-stenosed vessel both proximal and distal to the target lesion(s)
4. Patient has a reference vessel diameter between 4.0 and 6.5 mm
5. The guidewire and delivery system must cross the target lesion(s) intraluminally
6. Patient has a patent popliteal artery ($<50\%$ stenosis) distal to the target vessel
7. Patient has at least 1 patent infrapopliteal runoff vessel ($<50\%$ stenosis) not requiring intervention

CONFIDENTIAL INFORMATION

MD133246 Protocol Template

Revision#: 1

Doc Type: GC

8. Angioplasty balloon can be fully expanded in the target lesion during pre-treatment step

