5.1. Schedule of Events

Table 3: Schedule of Events

	Pre-Procedure ¹	Procedure	Discharge	Follow-Up Visit		
				30 Days	12, 24 & 36 Months	Unscheduled
Informed Consent	X					
Medical History and Demographics	X					
Height and Weight	X					
CBC	X					
Creatinine, serum	X					
beta-hCG test, if indicated	X within 7 days of study procedure					
ABI/TBI, resting ²	X		X	X	X	X
Rutherford Classification	X			X	X	X
Anti-Platelet/Anti-Coagulation Therapy Assessment	X		X	X	X	X
Clinical Inclusion/Exclusion	X					
Angiography		X		If indicated	If indicated	If indicated
Angiographic Inclusion/Exclusion		X				
Adverse Events	X	X	X	X		X
X-Ray ³	X ⁴				X	
Duplex Ultrasound ³				X	X	If indicated

1 Pre-procedure assessments required within 30 days of study procedure unless noted

2 If TBI used to qualify patient for study participation, TBI must be collected throughout duration of all study follow-up intervals.

3 Imaging sent to Core Lab for Assessment

4 Required imaging: X-ray image of non-covered stent(s) prior to deployment of Study Device AND X-ray image of Study Device post-deployment

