5.3. Pre-Screening/Screening

Patients who appear to meet clinical eligibility criteria via initial screening and review of existing medical records will be scheduled for a clinical evaluation. The informed consent must be signed prior to any study-related activity or procedure. All patients who sign an ICF will be considered entered into the screening phase of the study and should be recorded on the Screening and Enrollment Log.

The clinical evaluation must be performed within 30 days prior to the study procedure, unless noted, and will include:

- Informed consent
- Medical history and demographics
- Height and weight
- CBC
- Creatinine, serum
- b (beta)-hCG pregnancy testing within 7 days of the study procedure, if indicated
- ABI/TBI, resting (Note: If TBI is used to qualify patient for study participation, TBI must be collected throughout duration of all study follow-up intervals)
- Rutherford Classification
- Anti-platelet/anti-coagulation therapy assessment
- Review of clinical inclusion and exclusion criteria

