All areas that were pre-dilated should be covered with the study device. In addition, the study device should extend into healthy vessel a minimum of 1 cm proximal and distal to the target lesion(s). If overlapping devices is required to ensure complete coverage, there should be at least 1 cm of overlap between devices and device diameters should not differ by more than 1 mm. Post-dilation should be performed after each study device deployment to ensure seating against the vessel wall.

Procedural Completion Imaging

Final post-procedure angiogram will be performed to assess technical results. A post-procedure image is required. This image can be captured during final angiogram (X-ray shot without contrast) or by plain film X-ray. Imaging will be sent to the Core Lab for assessment.

Approved closure devices may be utilized at the Investigator's discretion. If a closure device is not used, sheath removal will be performed in accordance with institutional standard of care. Adequate hemostasis at the arterial puncture site as determined by the Investigator should be achieved prior to discharge.

Adverse events will be collected from the study procedure forward.

Discharge

Prior to discharge, a resting ABI/TBI will be measured. Discharge anti-platelet/anti-coagulation therapy and any additional adverse events will be documented.

Anti-platelet/Anti-coagulation Therapy

The Subject should be discharged and maintained on anti-platelet/anti-coagulation therapy at a dosage deemed appropriate by the Investigator.

CONFIDENTIAL INFORMATION

MD133246 Protocol Template

Revision#: 1

Doc Type: GC

The following medication regime is recommended:

- Dual anti-platelet therapy should be continued for a minimum of 6 months including Clopidogrel 75 mg PO QD (Other members of the thienopyridine class of ADP receptor inhibitors may be prescribed in place of Clopidogrel if subject intolerant to Clopidogrel) and Aspirin 81 – 325 mg PO QD
- Aspirin 81 – 325 mg PO QD should be continued through study follow-up

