5.7. Follow-Up

All Subjects are required to return to the Investigator for follow-up evaluations at 30 days, 12, 24 and 36 months after the index procedure. The schedule of events is outlined in **Table 3**.

Follow-up visits will be scheduled at appointed times after the date of index procedure. The Sponsor recognizes that Subjects may not be able to return for follow-up visits on the exact date required. Thus, a period during which each visit is allowed (window) is presented in **Table 4**.

Table 4 Study Visit Windows

Follow-up Visit	Window
30 days	30 ± 7 days
12 months	365 ± 45 days
24 months	730 ± 45 days
36 months	1095 ± 45 days

The following data are required and will be collected at 30 days post-procedure:

- ABI/TBI, resting
- Rutherford Classification
- Anti-platelet/Anti-coagulant therapy assessment
- Adverse Events
- Duplex Ultrasound

The following data are required and will be collected at 12, 24 and 36 months post-procedure:

- ABI/TBI, resting
- Rutherford Classification
- Anti-platelet/Anti-coagulant therapy assessment
- Adverse Events

CONFIDENTIAL INFORMATION

MD133246 Protocol Template

Revision#: 1

Doc Type: GC

- X-ray
- Duplex Ultrasound

The following data is required and will be collected at any Unscheduled Study-Related Visit or

- ABI/TBI, resting
- Rutherford Classification
- Anti-platelet/Anti-coagulant therapy assessment
- Angiography, if indicated
- Adverse Events
- Duplex Ultrasound, if indicated

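### Is it a flaw that TBI is collected on subjects who qualify by it, while the readable analysis plan summarises only change in ABI?

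*SAP*

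**What the plan says.** **Entry.** Protocol 4.2 (clinical inclusion criterion 5) requires an ABI of 0.9 or less, with an alternative: "If ABI > 0.9 or not measureable, patient is eligible for study if toe-brachial index (TBI) is ≤ 0.5".

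**Collection.** For subjects who enter by that route, footnote 2 of the Schedule of Events (Protocol 5.1) states that "TBI must be collected throughout duration of all study follow-up intervals", and Protocol 5.3 repeats the rule. At discharge, "Prior to discharge, a resting ABI/TBI will be measured" (Protocol 5.5). The scheduled and unscheduled visits in Protocol 5.7 list the item as "ABI/TBI, resting".

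**Endpoint.** The only pressure-index endpoint in the Protocol Summary and Protocol 3.2.3 is "Change in Ankle-Brachial Index from pre-procedure at 30 days, 12, 24 and 36 months".

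**Analysis.** Protocol 10.2.7 and SAP 2.5.7 call for descriptive statistics of the change from the pre-procedure value. SAP 5.5.7 includes "All subjects from both the ITT and PP populations which have their ABI measured at the corresponding visit" and defines change as the post-procedure value minus the pre-procedure value. None of the three separates subjects by entry route. TBI is defined in Protocol 3.2.1 and SAP 2.3, but no readable analysis section uses it.

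**The concern.** The protocol makes TBI mandatory for a defined group, and the readable plan shows no output for it. Within that group the change-in-ABI table seems to go wrong in two ways:

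- A subject whose baseline ABI could not be measured has no change in ABI and drops out of the table.
- A subject with a measured baseline ABI above 0.9 may have little room to improve on ABI, and is averaged with ABI-qualified subjects without being identified.

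If the group were large, a reader could take a small mean change for a weak haemodynamic result when it reflected the mix of subjects. The reader would also not see whether the measure that qualified these subjects had changed.

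**Working it through.** **1. Does the analysis match the endpoint?** Protocol 3.2.3 names change in ABI at 30 days and at 12, 24 and 36 months. SAP 5.5.7 tabulates change in ABI for everyone with an ABI at the visit. The two agree. No endpoint promises a combined index or a result for TBI.

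**2. Is a needed rule missing?** Change is post minus pre. Without a pre-procedure ABI it cannot be calculated, so the subject cannot contribute. No imputation or responder denominator depends on this subject.

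**3. Does collecting a measure oblige the plan to have an endpoint for it?** The protocol does not work that way elsewhere. ABI itself is taken at discharge, yet the endpoint begins at 30 days. Anti-platelet and anti-coagulation therapy is assessed at every visit and has no listed endpoint.

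**4. Can the absence of a TBI output be established?** No. Additional Analysis (Protocol 10.3, SAP 2.6 and 5.6) and the lists of tables, listings and figures (SAP 7.1 to 7.3) are redacted or not shown. A TBI summary, or a baseline table with counts by entry route, would normally be found there. The TBI definition in SAP 2.3 is compatible with such an output but does not prove one.

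**5. How large could the mixing be?** The plan has no figure to reproduce. Only the 108 subjects and the visit schedule come from the documents; everything else here is assumed.

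- q = share entering on TBI, 5% to 30%
- u = share of these with non-measurable ABI, 25% to 75%
- d1 = mean ABI change in ABI-qualified subjects, 0.25
- d2 = mean ABI change in TBI-qualified subjects with measured baseline ABI, 0 to 0.30

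TBI-qualified subjects: 108 × 0.05 = 5.4 to 108 × 0.30 = 32.4, so about 5 to 32.

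Subjects with no change in ABI (108qu): 108 × 0.05 × 0.25 = 1.4 to 108 × 0.30 × 0.75 = 24.3, so about 1 to 24.

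TBI values at baseline, discharge and four follow-up visits: 5 × 6 = 30 to 32 × 6 = 192, before missed visits.

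The share of analysed subjects with measured baseline ABI above 0.9 is f = q(1 − u)/(1 − qu), if ABI is also recorded on them at follow-up; otherwise f = 0. The all-subjects mean is (1 − f)d1 + f·d2.

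| q | u | f | d2 | All-subjects mean | Against d1 = 0.25 |
|---|---|---|---|---|---|
| 30% | 25% | 0.225/0.925 = 24.3% | 0 | 0.757 × 0.25 = 0.189 | 24.3% lower |
| 20% | 50% | 0.10/0.90 = 11.1% | 0.05 | 0.222 + 0.006 = 0.228 | 8.9% lower |
| 30% | 25% | 24.3% | 0.30 | 0.189 + 0.073 = 0.262 | 4.9% higher |
| any | any | any | 0.25 | 0.250 | none |
| any | any | 0 | any | 0.250 | none |

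The 24% figure needs the largest assumed TBI share, the smallest assumed non-measurable share, ABI recorded at follow-up, and no ABI change at all in these subjects. Even then, 0.189 is a correct mean for the population that SAP 5.5.7 describes.

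**6. Would separate rows be more informative?** Only slightly. The row for measured baseline ABI above 0.9 could hold 1 subject (108 × 0.05 × 0.25 = 1.4, at u = 75%). For mean TBI change with an assumed SD of 0.15 to 0.20, the 95% half-width t × SD/√n is 0.19 to 0.25 at n = 5 and 0.05 to 0.07 at n = 32. If the qualifying reading also serves as baseline, selection on TBI of 0.5 or less brings regression to the mean. In a single-arm study this cannot be told apart from improvement.

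**The case for a change.** The strongest argument for the concern is that the protocol itself treats TBI as the relevant index for these subjects and requires it at follow-up, so a plan that reports only ABI leaves their haemodynamic course unseen. The sections that define change in ABI are readable, and they contain no split by route. The selection sentence in SAP 5.5.7 also admits a subject who has an ABI at follow-up but none at baseline, and it does not say how to count that subject. A count by entry route would take one line.

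Some of this stands. The readable text names only ABI, the visit lists do not settle whether ABI is also recorded on TBI-qualified subjects, and a count of subjects without a measurable baseline ABI would help a reader. But the loose selection sentence is resolved by the definition of change, and it alters no result. SAP 5.5.7 gives its statistics as a minimum, and SAP 7 does the same for its outputs, so such a row can be added without changing the plan. TBI-qualified subjects also still contribute Rutherford category and duplex patency results.

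**Conclusion.** The concern does not hold. Change in ABI is a descriptive secondary endpoint, SAP 5.5.7 analyses it as listed, and its mean is not biased for what it claims to estimate. Primary patency at 12 months and the 30-day safety endpoint are untouched. A separate TBI summary would be a reasonable supplement, but its absence from the readable text contradicts no rule and distorts no stated result. Nor can the plan be said to lack one while the sections that would contain it are hidden.

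The possible difference between the all-subjects and ABI-qualified means, from 24% lower to 5% higher and including zero, rests on assumed shares and assumed changes. It describes case mix and is not evidence of error. The conclusion would be different if an endpoint promised a result on TBI or a denominator counted these subjects as failures; the readable text does neither.
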